11.2 Adverse Events

An AE is any untoward medical occurrence associated with the use of a drug, whether or not considered drug-related. An AE can therefore be any unfavorable and unintended sign (including a clinically significant abnormal laboratory finding), symptom, or disease temporally associated with the use of a medicinal (investigational) product, whether or not related to the trial treatment.

Medical conditions present at Screening (ie, before informed consent is obtained) or present before the first trial treatment (Day 1) are not AEs and are not recorded on the AE CRF. These medical conditions should be adequately documented on the Medical History CRFs. Any increase in severity or frequency of a medical condition documented as medical history after the first trial treatment will be recorded as an AE and will be captured on the AE CRF.

Progression of the cancer under study is not considered an AE or SAE and should not be reported as an AE or SAE.

An uncomplicated pregnancy is not an AE or SAE and should not be reported as an AE/SAE. Patients should be followed as described in Section 11.5.

The reporting period for all non-serious AEs begins at the time of the first trial treatment (Day 1) through 28 days after last dose of trial treatment. Patients who are withdrawn due to an AE should have an AE assessment completed 28 days or more after their last trial treatment. All AEs will be captured on the AE CRF.

AEs should be documented in terms of a single medical diagnosis. When this is not possible, the AE should be documented in terms of signs and/or symptoms observed by the investigator or reported by the patient at each trial visit.

The investigator will follow all related AEs observed during the trial until the AEs are considered resolved or until 28 days after last dose of trial treatment or the patient begins new anti-cancer therapy, whichever is earlier. Dynavax or the Dynavax designee may request additional follow-up on specific unresolved events.

11.2.1 Events of Clinical Interest

Selected non-serious and serious adverse events are also known as ECIs and must be reported to the sponsor.

ECIs must be reported following the reporting period for AEs (the initiation of study treatment through 28 days after permanent discontinuation of trial treatment) or, if they qualify as an SAE, following the reporting period for SAEs (through 90 days following cessation of trial treatment or EOS (whichever is later), or 28 days following cessation of trial treatment if the patient initiates new anti-cancer therapy). Any ECIs (as defined in this section) or follow up to an ECI that occurs in any patient **must be reported to Dynavax or its designee within 24 hours of investigator awareness of the event** (regardless of whether the investigator assesses the event as probably or possibly related to study drug). Reporting must be made by electronic media and on the Safety Report Form (regardless of whether the investigator assessed the event as serious or not serious) per SAE reporting procedures. Electronic reporting procedures can be found in the electronic data capture (EDC) data entry guidelines. Safety reporting procedures can be found in the Investigator Trial File Binder (or equivalent).

ECIs for this trial include:

- 1) An overdose of SD-101 or pembrolizumab, as defined in Section [11.2.2](#).

OR

- 2) An elevated AST or ALT lab value that is greater than or equal to 3 X the ULN and an elevated total bilirubin lab value that is greater than or equal to 2 X the ULN and, at the same time, an alkaline phosphatase lab value that is less than 2 X the ULN, as determined by way of protocol-specified laboratory testing or UNS laboratory testing.*

*Note: These criteria are based upon available regulatory guidance documents. The purpose of the criteria is to specify a threshold of abnormal hepatic tests that may require an additional evaluation for an underlying etiology. The trial site guidance for assessment and follow up of these criteria can be found in the Investigator Trial File Binder (or equivalent).

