10.0 TRIAL PROCEDURES

NOTE: As of Amendment 9, trial procedures have been simplified. This section has been updated accordingly.

All tests and evaluations required at specified time points are listed in the Schedule of Trial Events ([Appendix 1](#) through [Appendix 4](#)). The results of these tests and evaluations must be entered in the patient's source document and also recorded on the patient's CRF. All other tests and evaluations, including disease assessment and safety monitoring, are to be performed at the discretion of the investigator per local standard of care; these data will not be collected or recorded on the patient's CRF. Adverse events should be reported through safety reporting as described in Sections 10.3.9 and 10.3.10.

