10.3.6 Safety Laboratory Assessments

Laboratory assessments are listed below and will be performed according to the Schedule of Trial Events ([Appendix 1](#) through [Appendix 4](#)). Sample collections prior to injection and infusion on treatment days are preferred; however, these samples are allowed to be obtained the day prior to dosing. Routine laboratory tests (serum chemistry, hematology) for screening, including pregnancy testing may be obtained per standard of care and used for screening laboratory and determination of study eligibility as long as obtained within 28 days of first dose of pembrolizumab. Laboratories obtained within 7 days of Day 1 visit, with the exception of a CBC with ANC, do not need to be repeated on Day 1.

- Hepatitis and HIV testing at Screening Visit: serum hepatitis B, hepatitis C, and HIV testing per institutional standard of care as determined by laboratory tests for HBsAg, anti-HBc, and anti-HBs; anti-HCV; and anti-HIV -1/2, respectively

- Chemistry: sodium, potassium, chloride, bicarbonate, blood urea nitrogen (BUN), creatinine, glucose, calcium, AST, ALT, LDH, bilirubin, alkaline phosphatase, and C-reactive protein (CRP)
- Hematology: hemoglobin, hematocrit, white blood cell count with differential, and platelet count
- Thyroid function tests: free T3, free T4, and thyroid stimulating hormone (TSH)
- Coagulation: PT and aPTT
- Reserve serum aliquot specimens will be collected and stored frozen for possible future testing.
- Urinalysis with microscopy

Additional details for specific tests are provided in the Laboratory Manual.

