Demographics/Medical history/Prior medications ^g	X	X																										
Vital signs ^h	X	As of Amendment 9, per local standard of care at the discretion of the investigator.																										
Physical examination ⁱ	X																											
ECOG Performance Status	X																											
12-Lead ECG ^j	X																											
Review AEs ^k		X	X	X	X	X	X		X	X	X	X	X	X	X	X	X	X	X	X	X	X	X	X	X	X	X	
Review SAEs	X	X	X	X	X	X	X		X	X	X	X	X	X	X	X	X	X	X	X	X	X	X	X	X	X	X	
Concomitant Medications ^l	X	X	X	X	X	X	X		X	X	X	X	X	X	X	X	X	X	X	X	X	X	X	X	X	X	X	
HIV, HPV status, and hepatitis testing ^m	X																											

APPENDIX 2: SCHEDULE OF TRIAL EVENTS (PHASE 2 EXPANSION COHORTS 1 AND 3 – ANTI-PD-1/L1 NAÏVE) – CLOSED (CONT'D)

Screening Through Day 421 (Cont'd)

Trial Period:	Screening	Trial Treatment																											
		(every week ± 1 day)						(every 3 weeks ± 3 days)						(every week ± 1 day)				(every 3 weeks ± 3 days)											
Day:	-28 to -1 ^a	1	22	29	30 ^{b,cc}	36	43	50	64	85	106	127	148	169	190	211	232	253	260	267	274	295	316	337	358	379	400	421	
Study Procedures																													
Serum chemistry and CRP ⁿ	X	As of Amendment 9, per local standard of care at the discretion of the investigator.																											
Hematology ^o	X																												
Coagulation ^p	X																												
Thyroid function tests ^q	X																												
Urinalysis with microscopy																													
Pregnancy testing ^r	X																												
Efficacy Measurements																													
Clinical assessment of superficial lesions ^y	X	As of Amendment 9, per local standard of care at the discretion of the investigator.																											
Radiographic imaging ^z	X																												
Drug Administration and Observation																													
Pembrolizumab therapy ^{aa}		X	X				X		X	X	X	X	X	X	X	X	X	X			X	X	X	X	X	X	X	X	
SD-101 intratumoral injection ^{aa}			X	X		X	X		X	X	X	X	X	X	X			X	X	X	X	X	X	X	X	X	X	X	
SD-101 post-treatment observation ^{cc}			X	X		X	X		X	X	X	X	X	X			X	X	X	X	X	X	X	X	X	X	X	X	
Injection-site reaction assessment ^k			X	X		X	X																						
Tumor Biopsies																													
Tumor biopsies (consent required) ^{dd}	X							X			X				X														

APPENDIX 2: SCHEDULE OF TRIAL EVENTS (PHASE 2 EXPANSION COHORTS 1 AND 3 – ANTI-PD-1/L1 NAÏVE) – CLOSED (CONT'D)

Day 442 Through End of Study

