NOTE: As of Amendment 9, Phase 2 of the trial has been modified to continue dosing per protocol; however, efficacy and exploratory endpoints will no longer be collected, and the collection of safety endpoints has been simplified. The final study visit will be the EOS/Safety Follow-up. All other procedures to monitor disease progression and safety should be performed at the investigator's discretion according to local standard of care; these data do not need to be collected on the CRE. This Schedule of Trial Events has been amended and assessments that are no longer required have been deleted.

Screening Through Day 358

Trial Period:	Screening	Trial Treatment																						
		(every week ± 1 day)					(every 3 weeks ± 3 days)					(every 3 weeks ± 3 days)												
Day:	-28 to -1 ^a	1	8	9 ^{b,cc}	15	22	29	43	64	85	106	127	148	169	190	211	232	253	274	295	316	337	358	
Study Procedures																								
Informed consent	X																							
Inclusion/Exclusion Criteria	X																							
Demographics/Medical history/Prior medications ^g	X	X																						
Vital signs ^h	X	As of Amendment 9, per local standard of care at the discretion of the investigator.																						
Physical examination ⁱ	X																							
ECOG Performance Status	X																							
12-Lead ECG ^j	X																							
Review AEs ^k		X	X	X	X	X		X	X	X	X	X	X	X	X	X	X	X	X	X	X	X	X	
Review SAEs	X	X	X	X	X	X		X	X	X	X	X	X	X	X	X	X	X	X	X	X	X	X	
Concomitant medications ^l	X	X	X	X	X	X		X	X	X	X	X	X	X	X	X	X	X	X	X	X	X	X	
HIV, HPV status, and hepatitis testing ^m	X																							

APPENDIX 4: SCHEDULE OF TRIAL EVENTS (PHASE 2 EXPANSION COHORTS 5 AND 6 [ANTI-PD-1/L1 NAÏVE] AND COHORTS 7 AND 8 [ANTI-PD-1/L1 REFRACTORY OR RESISTANT]) (CLOSED) (CONT'D)

Screening Through Day 358 (Cont'd)

Trial Period:	Screening	Trial Treatment																					
		(every week ± 1 day)					(every 3 weeks ± 3 days)					(every 3 weeks ± 3 days)											
Day:	-28 to -1 ^a	1	8	9 ^{b, ee}	15	22	29	43	64	85	106	127	148	169	190	211	232	253	274	295	316	337	358
Serum chemistry and CRP ⁿ	X	X	X		X	X		X	X	X	X	X	X	X	X	X	X	X	X	X	X	X	X
Hematology ^o	X	As of Amendment 9, per local standard of care at the discretion of the investigator.																					
Coagulation ^p	X																						
Thyroid function tests ^q	X																						
Urinalysis with microscopy																							
Pregnancy testing ^r	X																						

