APPENDIX 1-4 FOOTNOTES (CONT'D)

Review AEs ^k	In Phase 1, assessments of injection-site reactions will be collected for a minimum of 90 minutes through the first 4 weekly injections and for 30 minutes following the remaining injections of SD-101 at the clinical site. Injection-site reactions will be graded based on the Toxicity Grading Scale for Healthy Adult and Adolescent Volunteers Enrolled in Preventive Vaccine Clinical Trials (Appendix 5). In Phase 2, injection-site reactions that persist for more than 7 days will be recorded as AEs. All other AEs and laboratory safety measurements will be graded per NCI CTCAE Version 4.03. All AEs, whether gradable by CTCAE or not, will also be evaluated for seriousness. AEs will be collected through 28 days after the last dose of trial treatment.
Concomitant medications ^l	All concomitant medications taken by the patient from Screening through the EOS visit will be reported.
HIV and hepatitis testing ^m	Serum hepatitis B, hepatitis C, and HIV testing as determined by laboratory tests for HBsAg, anti-HBc, and anti-HBs; anti-HCV; and anti-HIV -1/2, respectively. For HNSCC patients only, HPV status (positive + or negative) at Screening will be determined from either archival test results or new testing.
Serum chemistry and CRP ⁿ	Per local standard of care at the discretion of the investigator.
Hematology ^o	Per local standard of care at the discretion of the investigator.
Coagulation ^p	Per local standard of care at the discretion of the investigator.
Thyroid function tests ^q	Per local standard of care at the discretion of the investigator.
Pregnancy testing ^r	For WOCBP, serum or urine pregnancy test must be negative within 72 hours prior to the first trial treatment. If the urine test is positive or cannot be confirmed as negative then a serum test is required which must be negative for the patient to enroll. Dipstick can be used. Additional pregnancy testing should be scheduled per local regulations where applicable. All female patients are considered to be WOCBP except if they have been postmenopausal for at least 2 years or surgically sterile for at least 1 year.
Blood for IFN-alpha inducible gene expression (pharmacodynamic) ^s	Phase 1 Dose Escalation Cohorts 1-4 only: IFN-inducible gene expression measured at pre-dose on Day 1 (baseline), at Day 8 prior to injection, and at Day 9 which is 24 hours after injection.

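### The hepatic event of clinical interest counts only protocol-specified or unscheduled-visit tests, so after Amendment 9 a qualifying non-serious result from a routine local draw can miss the 24-hour report

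*Protocol*

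**What the plan says.** Protocol Section 11.2.1 lists two ECIs. The second is hepatic and needs three findings together: "An elevated AST or ALT lab value that is greater than or equal to 3 X the ULN", total bilirubin at or above 2 x ULN, and alkaline phosphatase below 2 x ULN. The definition closes by naming which tests count: "as determined by way of protocol-specified laboratory testing or UNS laboratory testing". Any ECI, serious or not and related or not, "must be reported to Dynavax or its designee within 24 hours of investigator awareness of the event". The synopsis safety text, updated for Amendment 9, still says that ECIs will be collected.

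Section 10.3.6 lists the chemistry panel, which contains all four analytes: "Laboratory assessments are listed below and will be performed according to the Schedule of Trial Events".

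Appendices 2 and 3 replace the chemistry marks between Screening and the End-of-Study visit with "As of Amendment 9, per local standard of care at the discretion of the investigator". Appendix 4 does the same from Day 379. From Day 1 to Day 358, however, the Appendix 4 row "Serum chemistry and CRP" still carries marks at the dosing visits, while footnote n, attached to that row, reads "Per local standard of care at the discretion of the investigator". Section 10.0 says that tests and evaluations outside the schedule "are to be performed at the discretion of the investigator per local standard of care; these data will not be collected or recorded" on the CRF, and sends adverse events to Sections 10.3.9 and 10.3.10.

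**The concern.** The ECI is a threshold rule. It brings a specific pattern of liver tests to the sponsor within 24 hours without waiting for a judgement on seriousness or cause. Its list of qualifying tests assumes that scheduled chemistry is being done. Amendment 9 removed most of that chemistry but left the list unchanged. A site following Section 11.2.1 literally could find a result over the threshold on a routine local draw and conclude that no ECI report is due.

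At stake are the timeliness of a liver signal while patients remain on treatment, and even ascertainment across sites. Sites treating Cohorts 5-8 also have two instructions for the same chemistry row, so the same result could be an ECI at one site and not at another.

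**Working it through.** No power or sample-size figure is involved. The check counts visits from the schedule columns and then compares the reporting routes.

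**Visits with required chemistry under Amendment 9**

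- Three-weekly visits, Day 43 to Day 358: (358 - 43)/21 + 1 = 16. Adding Days 1, 8, 15 and 22 gives 20.
- Three-weekly visits, Day 379 to Day 715: (715 - 379)/21 + 1 = 17.
- Pembrolizumab visits, Day 1 to Day 715: (715 - 1)/21 + 1 = 35.

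| Phase 2 group and period | Required by the table | Required by footnote n |
|---|---|---|
| Cohorts 1-4, Day 1 to 715 (Appendices 2, 3) | 0 of 35 pembrolizumab visits | 0 |
| Cohorts 5-8, Day 1 to 358 (Appendix 4) | 20 of 20 SD-101 dosing visits | 0 |
| Cohorts 5-8, Day 379 to 715 (Appendix 4) | 0 of 17 | 0 |

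The first and third rows give the same answer whichever instruction governs; only the second depends on the conflict. Chemistry is also marked at the End-of-Study and unscheduled visits, although footnote n read literally makes those discretionary too.

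**What happens to a result that meets all three criteria**

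| How it arises and is judged | Route | 24-hour clock |
|---|---|---|
| Test at an unscheduled visit | ECI (11.2.1) | Yes |
| Any test, event serious | SAE (10.3.10, 11.3.2) | Yes |
| Routine local draw, non-serious, clinically significant | AE on the CRF (11.2) | No |
| Routine local draw, non-serious, not judged clinically significant | None stated | No |

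The last two rows are the gap. The ECI list would have supplied the clock, but the draw is neither scheduled by the protocol nor made at an unscheduled visit.

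**Whether another rule closes the gap**

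- Section 7.6 permanently stops SD-101 at Grade 3 AST or ALT above 5 x ULN or Grade 3 bilirubin above 3 x ULN. The ECI begins at 3 x and 2 x, so a result can meet the ECI without reaching either of those figures.
- Section 7.6 also asks for missed chemistry listed in the schedule when SD-101 is delayed by more than 3 days. In Appendices 2 and 3 no on-treatment chemistry is now listed.
- Section 10.2 requires SAE reports during extended pembrolizumab treatment but not eCRF entry of laboratory results.
- SAP Section 9.7.4 summarizes only neutrophils, lymphocytes and platelets and produces no laboratory listings, relying on AE data for significant findings. The planned outputs would not recover a missed result.

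**Patients exposed**

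Planned enrolment in Protocol Section 4.1 is 60 + 25 + 25 + 25 = 135 (Cohorts 1-4) and 25 + 25 + 25 + 50 = 125 (Cohorts 5-8), 260 in all. The documents do not say how many were still on treatment when Amendment 9 took effect.

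**The case against.** A reader might infer that the most serious liver events would go unreported. The documents do not support that. A clinically significant laboratory abnormality is an adverse event and goes on the CRF (Section 11.2). A serious one, including an important medical event, carries a 24-hour clock whatever test revealed it. Section 10.0 preserves both routes in the same paragraph that stops collection of other data. What is lost is the ECI route and its clock for a non-serious result.

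A reader might also infer that Cohorts 1-4 have no protocol-directed liver testing at all. That is too absolute. Table 7-1 calls for liver function monitoring once AST, ALT or bilirubin is raised, and a safety concern should prompt an unscheduled visit, where results count. These routes narrow the gap, but unscheduled-visit procedures are discretionary (Section 10.9), and neither route clearly covers the routine draw that first shows the abnormality.

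No sentence expressly excludes standard-of-care results, and a site could argue that a test mentioned in the schedule is protocol-specified even when discretionary. Section 11.2.1 also refers to site guidance that is not among the documents. Exclusion is therefore an inference, although it is the natural reading because Section 10.0 separates schedule-required tests from all others.

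Finally, 135 of 260 is not a count of affected patients. Cohorts 1-4 closed to enrolment at Amendment 6. Suppose their last patient started no later than the Amendment 8 date, 08 February 2018, with no delays. SD-101 would then end by Day 421, 420 days later (04 April 2019), and pembrolizumab by Day 715, 714 days later (23 January 2020). The Amendment 9 date is not shown, and the SAP of 04 November 2019 still cites Amendment 8. It is therefore not established that Cohorts 1-4 were still receiving both drugs. Equally, the status table marks them Closed rather than Complete, so it does not show that all had finished. This objection to the size stands.

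**Conclusion.** The mismatch is real. Section 11.2.1 ties the hepatic ECI to tests that Amendment 9 largely stopped requiring. Read as written, a qualifying but non-serious result from a routine local draw can miss 24-hour ECI reporting. For Cohorts 1-4 on treatment, and for Cohorts 5-8 from Day 379, this holds under either reading of the schedule. For Cohorts 5-8 up to Day 358 it holds only if footnote n governs; if the row governs, the definition works at those 20 visits.

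The consequence is delayed or uneven reporting of non-serious results, not loss of serious liver events. The number of patients exposed is unknown, with planned enrolment as the upper limit. The conclusion assumes that discretionary local tests are not protocol-specified and that the unseen site guidance does not already widen the definition. It should be corrected while any patient remains on treatment.

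**What to change.** In Section 11.2.1, extend the qualifying test source to any laboratory result known to the investigator, expressly including local standard-of-care testing. The thresholds and the 24-hour clock stay as they are.

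Separately, the sponsor must reconcile the Appendix 4 chemistry row with footnote n, and bring Sections 7.6, 10.0 and 10.3.6 into line with the result. Which instruction should govern is for the sponsor to settle; no testing schedule is proposed here.

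The cost is a clarification letter or a short amendment, and notice to sites. The change to Section 11.2.1 adds no tests and alters no dose or treatment rule. It may produce some additional expedited reports.

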11.2.2 Overdoses

An overdose of SD-101 is defined as more than twice the protocol-specified dose.

An overdose of pembrolizumab is defined as ≥ 1000 mg (≥ 5 x the prescribed dose).

An overdose of SD-101 or pembrolizumab, regardless of the presence of an associated AE or SAE, is considered an ECI and must be documented and reported according to the ECI requirements described in Section 11.2.1.

Additionally, an AE or SAE associated with an overdose of SD-101 or pembrolizumab must be documented and reported according to the respective requirements for AEs or SAEs.

11.2.3 New Cancer (Not the Cancer Being Investigated Under the Study)

Any new non-serious or serious cancer (not the cancer being investigated under the study), whether or not the new cancer is related to the trial treatment (SD-101 and/or pembrolizumab), **must be reported to Dynavax or its designee within 24 hours of investigator awareness of the event per SAE reporting procedures.**

The occurrence of any non-serious new cancer will follow the reporting period for AEs (Section 11.2) and the occurrence of any serious new cancer will follow the reporting period for SAEs (Section 11.3).

11.2.4 Definition of Adverse Reaction

An AR is defined as any AE caused by the use of a pharmaceutical product. ARs are a subset of all suspected AEs for which there is reason to conclude that the pharmaceutical product caused the event.

